5.5.3.2 Other Secondary Efficacy Endpoints

5.5.3.2.1 TSC-associated Seizure Treatment Responders and TSC-associated Seizure Freedom

Blinded Phase:

The number of patients experiencing a $>25\%$ increase, ≥ 0 to $\leq 25\%$ increase, >0 to $<25\%$ reduction, ≥ 25 to $<50\%$ reduction, ≥ 50 to $<75\%$ reduction or $\geq 75\%$ reduction in TSC-associated seizure frequency from baseline during the treatment period will be summarized by treatment arm.

In addition to the key secondary endpoint, the proportion of patients considered treatment responders, defined as those with a $\geq 25\%$ or $\geq 75\%$ reduction in TSC-associated seizure frequency from baseline and the proportion of patients who are TSC-associated seizure free, defined as those with a 100% reduction in TSC-associated seizure frequency from baseline, during the treatment period, for patients who have not withdrawn from the trial

during the treatment period will be summarized by treatment arm and analyzed using a CMH test stratified by age as described in Section 5.5.3.1.1.

Additionally, the proportion of patients responding will be presented graphically, by treatment arm, by plotting the percent reduction against the cumulative proportion of patients achieving that level of reduction. The x-axis will be the percent reduction from baseline and the y-axis will be the proportion of patients with at least that amount of reduction, i.e. $y = \Pr(X \geq x)$.

Sensitivity analyses will be performed on the ITT analysis set, repeating the above analysis, using data for only the maintenance period, titration period, and during each 4 weeks of the maintenance period (Week 1 to 4, Week 5 to 8 and Week 9 to 12 of the 12 week maintenance period).

Analyses on the maintenance period, titration period and by each 4 weeks of the maintenance period will include only patients who have at least 7 days of seizure data within each period.

Open-label Extension:

Descriptive summaries described above for the blinded phase will be repeated for OLE periods.

5.5.3.2.2 Number of TSC-associated Seizure Free Days

Blinded Phase Only:

The number of TSC-associated seizure free days during each period will be based on 28 day averages and calculated as:

$$\left(\frac{\text{Number of seizure free days in the period}}{\text{Number of reported days in IVRS in the period}} \right) \times 28$$

The change from baseline in TSC-associated seizure free days per 28 days will be analyzed for the treatment period using an ANCOVA approach. The model will include baseline and stratified age group as covariates and treatment arm as fixed factor.

The estimated least squares means, treatment difference, together with the 95% CIs and p-value will be presented.

The analysis will be repeated for the maintenance period.

5.5.3.2.3 Other Seizures

Blinded Phase:

For other seizures (see Section 5.1.3.8), summaries and analyses will be performed as per the primary endpoint (Section 5.5.2). Patients with no seizures during the baseline period, for a particular seizure type, will be excluded from the analysis of that seizure type.

Other seizure and total seizure responders and freedom will also be summarized and analyzed using the methods described in Section 5.5.3.2.1. However, the summaries and analyses during the maintenance and titration periods and during each 4 weeks of the maintenance period will be produced for total seizures only. Patients with no corresponding other seizures during the baseline period will be excluded from the analysis for other seizures.

Open-label Extension:

Descriptive summaries described above for the blinded phase will be repeated for OLE periods.

5.5.3.2.4 Quality of Life in Childhood Epilepsy (2–18 Years)

Blinded Phase:

The QOLCE is a parent-reported questionnaire that evaluates health related quality of life in children aged 2–18 years old. It contains 76 items with 16 subscales covering 7 domains of life function: Physical activities, social activities, cognition, emotional well-being, behavior, general health, and general quality of life.

All items in the questionnaire are rated on a 5-point or 6-point categorical scale. Based on the responses to the items in each domain, scores for 16 subscales are derived. The subscales are presented in Table 4.

Table 4 QOLCE Subscales

Subscale	Item Domains	Items Used
Physical Restrictions	Physical Activities	3.1 (a to j)
Energy/Fatigue	Physical Activities	3.2 (a,b)
Attention/Concentration	Cognition	5.1 (a,d,e,f,g)
Memory	Cognition	5.1 (j,k,l,m,n,o)
Language	Cognition	5.1 (p,q,r,s,t,u,v,w)
Other Cognitive	Cognition	5.1 (b,c,h)
Depression	Emotional Well-Being	4.1 (a,d,e,l)
Anxiety	Emotional Well-Being	4.1 (b,g,j,n,o,p)
Control/Helplessness	Emotional Well-Being	4.1 (c,f,h,i)
Self-esteem	Emotional Well-Being	4.1 (k,m,q,r,s)
Social Interactions	Social Activities	6.1 (c,f,h)
Social Activities	Social Activities	6.1 (a,e) and 6.2
Stigma Item	Social Activities	6.1 (i)
Behavior	Behavior	7.1 (a,c,f,g,h,i,j,k,l,m,o,q,r,s,t)
General Health Item	General Health	8.1
Quality of Life Item	Quality of Life	9.1

Items within each subscale will be coded and linearly transformed, according to the methods of Sabaz et al.¹, to a score of 0 to 100, where 0 represents the lowest or poorest category and 100 represents the highest level of functioning.

A subscale score is calculated for each subscale by computing the mean of the items within the subscale. An ‘Overall Quality of Life Score’ can be calculated by taking the mean of the subscale scores.

Individual items will be listed only. The subscale scores and the overall quality of life score, recorded at each visit, will be summarized, on a continuous scale, by treatment arm. The change from baseline will also be included.

The change from baseline to the end of treatment visit, for the overall quality of life score, and the attention/concentration, memory, language, other cognitive, social interactions and behavior subscale scores only, will be analyzed using analysis of covariance (ANCOVA). The model will include baseline and stratified age group as covariates and treatment arm as fixed factor.

The estimated least squares means, treatment difference, together with the 95% CIs and p-value will be presented. Exploratory analyses may also be performed on other subscale scores.

Missing data will be handled according to Section 5.1.1.2.1.

The QOLCE was to be completed for patients aged 2-18 years old only. The primary analysis will be based on all patients who have a completed questionnaire, regardless of age. Summaries and analyses will be repeated using questionnaires only from patients who were aged 2 to 18 years old at the time of informed consent.

The individual responses will not be listed, only the derived information for each derived score will be listed.

Open-label Extension:

Descriptive summaries described above for the blinded phase will be repeated for OLE visits.

5.5.3.2.5 Quality of Life in Epilepsy, Version 2 (19 Years and Above)

Blinded Phase:

The QOLIE-31-P is a survey of health-related quality of life for adults with epilepsy. It comprises 38 questions about health and daily activities and also includes questions designed to evaluate how much distress the patient feels about problems and worries related to epilepsy. The QOLIE-31-P will be administered to patients aged 19 years or older. Should the patient be unable to complete the QOLIE-31-P independently, it is permissible for their caregiver to assist.

The questionnaire consists of the following 7 subscales: energy, mood, daily activities, cognition, medication effects, seizure worry, and overall quality of life. Each subscale consists of a number of questions in addition to a 'distress' item. The raw score for each question and the 'distress' item are converted to a 0-100 score according to the scoring manual² (higher scores reflecting greater well-being). The converted scores for each question within the subscale are then used to calculate a final subscale weighted score (higher scores reflect better quality of life; lower ones, worse quality of life) as follows:

$$\left(\frac{\text{Sum of converted scores for each question in the subscale}}{\text{Number of questions in the subscale}} + \text{'distress' item converted score} \right)$$

The total score (ranging from 0 to 100) is then calculated as:

$$\left(\frac{\text{Sum of all subscale weighted scores} + \text{Sum of all subscale 'distress' item converted scores}}{\text{Number of subscales}} \right) \times 100$$

Individual items will be listed only. The weighted subscale scores and the total score, recorded at each visit, will be summarized, on a continuous scale, by treatment arm. The change from baseline will also be included.

The change from baseline to the end of treatment visit, for the weighted subscale scores and the total score, will be analyzed using the same ANCOVA approach as specified in Section 5.5.3.2.4.

Missing data will be handled according to Section 5.1.1.2.2.

The QOLIE-31-P was to be completed for patients aged 19 years and above only. The primary analysis will be based on all patients who have a completed questionnaire, regardless of age. Summaries and analyses will be repeated using questionnaires only from patients who were aged 19 years or older at the time of informed consent.

The individual responses will not be listed, only the derived information for each derived score will be listed.

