5.1.1.2.2 Quality of Life in Epilepsy, Version 2 (19 Years and Above)

For missing questions within subscales, the following rule will be applied:

- For subscales containing 4 or more questions (not including the 'distress' item), apply the following:
 - If less than or equal to 50% of the questions within the subscale are missing then the converted score for the missing questions will be set to the average of the non-missing question converted scores.
 - If more than 50% of the questions within the subscale are missing then the subscale weighted score will be set to missing.
- For subscales containing less than 4 questions (not including the 'distress' item) the subscale weighted score will be set to missing.

For missing 'distress' items, the following rule will be applied:

- If the corresponding subscale weighted score is missing then no imputation is needed and the 'distress' item converted score will be missing.
- If the corresponding subscale weighted score is not missing then set to the average of the non-missing 'distress' item converted scores.

For missing subscale weighted scores or missing 'distress' item converted scores, the following rule will be applied when calculating the total score:

- If 3 or more of the 'distress' item converted scores are missing then the total score will be set to missing.
- If 3 or more of the subscale weighted scores are missing then the total score will be set to missing.

- If less than 3 'distress' item converted scores are missing and less than 3 subscale weighted scores are missing, then the total score will be calculated based on the available non-missing data, following the rules above.

Note: it is possible that a subscale weighted score is missing, but that the corresponding 'distress' item was answered and the converted score is not missing. Following the rules above, the total score would include the non-missing 'distress' item converted score in the calculation even though the corresponding subscale weighted score is missing and hence not included.

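### The printed QOLIE-31-P formulas give a total of 0 to 30,000 rather than 0 to 100, and keeping a distress score whose subscale is missing creates an artificial change from baseline

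*SAP*

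**What the plan says.** Section 5.5.3.2.5 sets out the scoring in four steps.

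- Structure: "The questionnaire consists of the following 7 subscales: energy, mood, daily activities, cognition, medication effects, seizure worry, and overall quality of life". Besides its questions, every subscale carries one distress item.
- Conversion: "The raw score for each question and the 'distress' item are converted to a 0-100 score according to the scoring manual". The manual (reference 2 in section 6) is cited for this step only.
- Subscale weighted score, as printed: "Sum of converted scores for each question in the subscale", divided by the number of questions in the subscale, plus the converted distress score.
- Total, as printed: the sum of the weighted subscale scores plus the sum of the distress scores, divided by the number of subscales, times 100. It is introduced by "The total score (ranging from 0 to 100) is then calculated as".

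Section 5.1.1.2.2 gives the missing-data rules. A total is still calculated, from whatever is available, when fewer than three subscale scores and fewer than three distress scores are missing. A closing note covers the case where a subscale score is missing but its distress item was answered: "the total score would include the non-missing 'distress' item converted score in the calculation even though the corresponding subscale weighted score is missing".

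The change from baseline in the weighted subscale scores and in the total is analyzed by ANCOVA, with confidence intervals and a p-value. Section 3.3.2 lists the QOLIE-31-P among the other (not key) secondary endpoints.

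**The concern.** A score built by adding quantities that each reach 100, and then multiplying by 100, cannot end at 100. The text speaks of a weighted score, yet in the printed formulas the distress item does not weight anything. It is added inside each subscale and added again in the total.

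The missing-data note is a separate problem. If a subscale leaves one term of the total while its distress item stays in another, the terms no longer cover the same subscales. A patient whose condition has not changed, but who has a subscale missing at only one of the two visits, then shows a change from baseline that reflects only the missing answers.

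At stake is the adult quality-of-life result. The SAP is the programming specification, so a program that follows it would produce scores off the stated scale, with distress given extra weight and with spurious changes where subscales are missing.

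**Working it through.** **Inputs** (section 5.5.3.2.5): 7 subscales, one distress item each. Write m for the mean of a subscale's converted questions and d for its distress score, both 0 to 100. The weighted score is W.

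**Range of the printed formulas**

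- W = m + d, so the maximum is 100 + 100 = 200.
- Total = (ΣW + Σd) / 7 × 100.
- All answers best: ΣW = 7 × 200 = 1,400 and Σd = 7 × 100 = 700, so total = (1,400 + 700) / 7 × 100 = 30,000.
- All answers worst: total = 0.

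The stated 0 to 100 is not reproduced; the printed maximum is 30,000 / 100 = 300 times larger.

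**Weight on distress.** Substituting W, total = (Σm + 2Σd) / 7 × 100. Each distress item has coefficient 200/7 and each subscale mean 100/7. Distress supplies 1,400 of the 2,100 possible summed points (67%).

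**Small changes to the printed form**

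- Drop the × 100: maximum (1,400 + 700) / 7 = 300.
- Drop the second distress sum: maximum 1,400 / 7 × 100 = 20,000.
- Drop both: maximum 1,400 / 7 = 200.

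Several other forms do give 0 to 100:

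- W = m + d with total (ΣW + Σd) / 2,100 × 100
- W = (m + d) / 2 with total ΣW / 7
- W = m with total ΣW / 7
- W = m × d / 100 with total ΣW / 7, or (ΣW / Σd) × 100
- W = m × d with total ΣW / Σd

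These are not all the same score, so the stated range does not identify the intended one.

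**Missing subscale, distress score kept.** Take an unchanged patient with every m and d equal to 50. Section 5.1.1.2.2 does not say whether the divisor stays at 7 or falls to the number available, so both are shown, together with the ratio form Σ(m × d) / Σd.

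| Form | Complete | One subscale missing | Two missing |
|---|---|---|---|
| Printed, divisor 7 | (700 + 350)/7 × 100 = 15,000 | (600 + 350)/7 × 100 = 13,571 (−9.5%) | (500 + 350)/7 × 100 = 12,143 (−19.0%) |
| Printed, divisor = available | 15,000 | (600 + 350)/6 × 100 = 15,833 (+5.6%) | (500 + 350)/5 × 100 = 17,000 (+13.3%) |
| Ratio form | 17,500/350 = 50 | 15,000/350 = 42.9 (−14.3%) | 12,500/350 = 35.7 (−28.6%) |

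All three rows give a false change. A divisor rescaled to the maximum of the terms present would avoid it for this patient: (600 + 350) / (6 × 200 + 7 × 100) = 950 / 1,900 = 0.5, as when complete. The SAP states no such divisor.

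**Same subscales in every term.** Dropping the distress item with its subscale gives (600 + 300) / 6 × 100 = 15,000 for the printed form and 15,000 / 300 = 50 for the ratio form. The false change disappears.

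**The case against.** The strongest objection is that the signs may not be the sponsor's. The formulas are display equations read from PDF by a program, and a multiplication or division sign could have been read as a plus. The term weighted score, the 0 to 100 range and the separate handling of distress scores would all suit a product or a ratio. This stands as a reason to look at the source page first. It does not dispose of the point: one changed sign does not by itself restore 0 to 100, and the note in section 5.1.1.2.2 is prose that no misread sign could have produced.

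Several stronger readings are tempting, and the SAP does not support them.

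- A reader might infer that missing content always lowers the score, by 9.5% or 19%. That assumes the divisor stays at 7, which the SAP does not say. With the available number as divisor the direction reverses.
- A reader might infer that the range and the word weighted require the ratio form. Several formulas give 0 to 100. With W = m × d the analyzed subscale scores would run 0 to 10,000, and the total would be 0/0 if all distress scores were 0.
- A reader might infer that the ANCOVA result would mainly reflect distress. A 67% share of the possible range does not show this, because influence on a change score depends on variances and covariances that are not given.

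It is also fair that a constant factor leaves p-values unchanged, although it rescales estimates and confidence intervals, and that totals in the thousands would be noticed at once. The doubled distress term and the missing-subscale effect are not constant factors. Either could survive a correction that only restored the scale.

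**Conclusion.** The point holds in two parts. As printed, the formulas give 0 to 200 per subscale and 0 to 30,000 for the total, and they enter each distress item twice. Nothing elsewhere in the SAP corrects them. This part depends on the signs being as they appear in the machine-read text.

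The second part does not depend on the signs. Keeping a distress score when its subscale score is missing creates an artificial change under the printed formula with either divisor and under the ratio form. The sizes shown are for one illustrative patient with all items at 50. Their direction depends on a divisor that the SAP leaves open, so no expected bias in a treatment comparison can be quoted.

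A reader might infer that the adult quality-of-life results were in fact mis-scored. The SAP cannot show that; it would follow only if the program implements the text as printed. The endpoint is outside the hierarchy in Table 3 of section 5.5.1 and intended for patients aged 19 and over, so primary and key secondary conclusions are not affected. The correction should be made because the rule feeds reported p-values and is cheap to repair.

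**What to change.** 1. Check the signs in both equations against the source page.
2. Restate both formulas in full from the cited scoring manual, so that all-best answers give a total of 100, and state the range of the weighted subscale score.
3. Compute the total over the same set of subscales in every term, including the divisor, so that a distress item is dropped when its subscale score is missing. Revise the closing note of section 5.1.1.2.2 to match.
4. State what is done if all distress scores are 0.
5. Test the scoring program on two cases: all-best answers must give 100, and a patient with all items equal must score the same with a subscale missing. Do not require equality for every unchanged patient. In the ratio form with all distress scores at 50, six means of 50 and one of 80 give (6 × 2,500 + 4,000) / 350 = 54.3 when complete. Dropping the subscale at 80 with its distress item gives 15,000 / 300 = 50.0, because the subscale means differ.

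The cost is SAP wording and a check of the scoring program. No new data are needed.

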5.5.3.2.6 Physician Global Impression of Change

Blinded Phase:

The PGIC comprises the following questions to be rated on a 7-point scale:

- Please assess the change in the patient's general functional abilities since Visit 3 (prior to the commencement of study medication).

The possible responses are: Very Much Improved; Much Improved; Slightly Improved; No Change; Slightly Worse; Much Worse; Very Much Worse.

The responses above are based on comparison with a brief description of the patient's overall condition used as a memory aid from Visit 3.

Each response will be coded with a score from 1 to 7, where 1 = Very Much Improved, and 7 = Very Much Worse.

The PGIC response/score, recorded at each visit, will be summarized separately, on both a categorical and continuous scale, by treatment arm.

The score at the end of treatment visit and last visit (if different to the end of treatment) will be analyzed using ordinal logistic regression. Proportional odds modelling will be carried out by including treatment arm as a factor. The estimated odds ratio (GWP42003-P vs. placebo), 95% CI for the odds ratio, and the p-value testing the null hypothesis that the odds ratio is equal to 1, will be presented. Analysis performed at the last visit will be considered the primary analysis for this endpoint, with the analysis at the end of treatment visit considered a sensitivity analysis.

Should the proportional odds assumption not hold, i.e. if the p-value for the score test for proportional odds assumption is <0.05 , then, as a sensitivity analysis, the scores will also be analyzed using a Cochran-Armitage trend test. This will be presented together with the results of the ordinal logistic regression.

Open-label Extension:

Descriptive summaries described above for the blinded phase will be repeated for OLE visits.

5.5.4 Exploratory Efficacy Endpoints

5.5.4.1 Composite Focal Seizure Score

Blinded Phase:

Composite focal seizure score will be calculated as the sum of:

- 1 × Number of focal motor seizures without impairment of consciousness or awareness.
- 2 × Number of focal seizures with impairment of consciousness or awareness.
- 3 × Number of focal seizures evolving to bilateral convulsive seizures.

Summaries and analyses of composite focal seizure score will be performed as per the primary endpoint (Section 5.5.2).

Sensitivity analyses will be performed on the ITT analysis set, repeating the above analysis, using data for only the maintenance period, titration period, and during each 4 weeks of the

maintenance period (Week 1 to 4, Week 5 to 8 and Week 9 to 12 of the 12 week maintenance period).

Analyses on the maintenance period, titration period and by each 4 weeks of the maintenance period will include only patients who have at least 7 days of seizure data within each period.

Open-label Extension:

Summaries will be performed for the OLE periods as described in the OLE portion of the primary endpoint section (Section 5.5.2).

5.5.4.2 Individual Seizure Types

Blinded Phase:

For each individual seizure type (focal motor seizures without impairment of consciousness or awareness, focal seizures with impairment of consciousness or awareness, focal seizures evolving to bilateral generalized convulsive seizures, tonic-clonic, tonic, clonic, atonic, absence, myoclonic and partial sensory seizures, and infantile or epileptic spasms), summaries will be performed as per the primary endpoint (Section 5.5.2). However, analyses will only be performed for the following seizure types:

- Focal motor seizures without impairment of consciousness or awareness;
- Focal seizures with impairment of consciousness or awareness;
- Focal seizures evolving to bilateral generalized convulsive seizures;
- Tonic-clonic; and
- Tonic.

Patients with no seizures during the baseline period, for a particular seizure type, will be excluded from the analysis of that seizure type.

Sensitivity analyses will be performed on the ITT analysis set, repeating the above analyses using data for only the maintenance period, titration period, and during each 4 weeks of the maintenance period (Week 1 to 4, Week 5 to 8 and Week 9 to 12 of the 12 week maintenance period).

Analyses on the maintenance period, titration period and by each 4 weeks of the maintenance period will include only patients who have at least 7 days of seizure data within each period.

Individual seizure type responders and freedom will also be summarized and analyzed using the methods described in Section 5.5.3.2.1, for the following seizure types only:

- Focal motor seizures without impairment of consciousness or awareness;
- Focal seizures with impairment of consciousness or awareness;
- Focal seizures evolving to bilateral generalized convulsive seizures;
- Tonic-clonic; and
- Tonic.

The summaries and analyses during the maintenance and titration periods and during each 4 weeks of the maintenance period will be produced. Patients with no corresponding seizures, for a particular seizure type, during the baseline period will be excluded from the analysis for that seizure type.

Open-label Extension:

Descriptive summaries described above for the blinded phase will be repeated for OLE periods.

